Preliminary information gained from this study will enable us to plan a prospective, large, national study using 4-OHT gel for breast cancer risk reduction that can be easily performed not only at academic but also non-academic institutions. Therefore, it is very important that we choose endpoints that are validated, easily measurable and do not require special and expensive technology. This future possibility was already discussed with and is supported and welcomed by the SWOG Cancer Prevention and Epidemiology Group.

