#### **13.1 Study Design/Description**

A total of 198 potentially eligible participants will be consented and screened for eligibility and, with a conservative estimate, 158 (80%) participants are expected to be eligible. These 158 women will be randomized 1:1 into one of two groups: placebo or 4-OHT gel 2 mg per breast. Treatment will last for 52 weeks. Considering an attrition rate of approximately 19%, we expect to have 128 evaluable women who will have both baseline and 52-week measurements of percent MD of the breast, 64 women in each group.

With 64 women in each group, we will have an 80% power to detect a decrease of percent MD of 6% in treatment group against 2% in placebo group, with a common standard deviation of 8%, using a two-sided t-test with a significance level of 0.05. The proposed difference between the active treatment and placebo groups and the standard deviation are based on conservative estimates from the published work by Cuzick et al. The sample size calculation is performed using nQuery + nTerim 3.0.

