#### **13.2 Randomization/Stratification**

Participants will be assigned a randomization number once the following has been accomplished: eligibility has been verified at the site level, eligibility has been confirmed by the site PI, and eligibility CRF has been entered into the DMI web application. The randomization number will be generated by the database and assigned to the participant.

A total of 158 women will be enrolled and randomized 1:1 into one of two groups. Treatment will last for 52 weeks. Considering an attrition rate of approximately 19%, we expect to have 128 evaluable women who will have both baseline and 52-week measurements of percent MD of the breast, 64 women in each group.

We will stratify the randomization by study site (UT MD Anderson Cancer Center, Dana Farber Cancer Institute, Northwestern University, Moffitt Cancer Center, University of Arizona Cancer Center, University of Minnesota, and University of Wisconsin) and baseline breast density category (heterogeneously dense (C), extremely dense (D)) using random permuted block design with the block size of 4.

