### 13.4 Primary Objective, Endpoint(s), Analysis Plan

The primary objective of this study is to evaluate the change in percent MD (using Cumulus software) from baseline to the week 52 in women applying 4 mg OHT gel versus placebo based on the intent-to-treat principle. The intent-to-treat population is defined as all participants who are randomized and have MD measurements from both baseline and 52 weeks. The primary analysis will be performed comparing the active group versus placebo group per randomization, regardless of the compliance of each participant.

The percent MD is the MD (percent dense area) that is visually estimated using both the mediolateral oblique (MLO) view and the craniocaudal (CC) view as the proportion of the total breast area that was composed of dense tissue (to the nearest 5%). For the study purpose, the densest breast will be the target lesion for the primary endpoint. Breast biopsy for secondary and exploratory endpoints will be performed in the opposite (non-target) breast.

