At the end of the study, all participants who have MD measurements from both baseline and 52 weeks, regardless of the compliance, will be included in the primary analysis. Change in percent MD of the breast from baseline to 52 weeks will be summarized using descriptive statistics, such as mean, standard deviation, median and range for each arm. With visual assessments of MD from both the MLO and CC views for evaluating the primary endpoint, Hotelling's  $T^2$  test will be used to conduct multivariate hypothesis testing which includes both views. Hotelling's  $T^2$  test represents the multivariate generalization to the independent two-sample t-test in the univariate setting. The correlation and variance-covariance matrix will be assessed to estimate the level of dependency between the MLO and the CC views. The mean change in percent MD at 52 weeks incorporating both the MLO and CC views will be compared between the two groups utilizing Hotelling's  $T^2$  test. Q-Q plots, used to visually assess the assumption of normality, will be constructed for the marginal distributions associated with observations emanating from both the MLO and the CC view. Assuming the mean difference in density between the observations between the 4-OHT and the placebo groups is approximately normally distributed, then the primary analysis will be conducted as previously described. Additionally, a 95% confidence ellipse (simultaneous confidence intervals) for the mean vector containing information from both views will be provided. If the change in density is not normally distributed, then we will try to rescale to achieve approximate normality by using the Box-Cox transformation. In our prior experience evaluating change in density in response to oral tamoxifen, change in density was scaled and raised to the 1.75th power to approximate normality. We will have to determine what power to use in the Box-Cox transformation based on the data that we have on hand. Transformations may be performed when necessary to make the measure of MD close to normal distribution before evaluating the change of MD over time between two groups. If the Hotelling's  $T^2$  test is significant, we will further examine whether the significant difference between the 4-OHT gel group and the placebo group is in the MLO view or the CC view or both. Note that the sample size calculation is based on the two-sample t-test. It provides a conservative estimate of the statistical power because the Hotelling's  $T^2$  test is more efficient than the two-sample t-test.

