
We will evaluate if the change of breast density is different in patients with heterogeneously dense (C) vs extremely dense (D) breast at baseline, by incorporating this covariate and its interaction with treatment over time in the repeated measures analysis.

Due to the COVID-19 closures of clinical research activities, a small number of participants (less than 20) will have their month 12 visits by telephone. These participants will continue the randomized treatments and have mammograms in the month 13-18 visits. The measurements of breast density from the month 13-18 (instead of month 12) visits will be used as the primary endpoint. We will first provide summary statistics for the breast density from the month 13-18 visits, from the month 12 visit, and then graphically explore any impact of potentially longer exposures of the treatment on the primary endpoint of mammographic breast density. If appropriate, we will incorporate the timing of the measurement as a covariate in the analysis to estimate the effect of prolonged exposure of the treatment on mammographic breast density. We will also perform a sensitivity analysis by including month 13-18 measures as primary endpoint, and by excluding month 13-18 measures to evaluate the impact of the different timing of measurements on the primary endpoint analysis. For the sample size calculation, we have factored in a 19% inevaluable rate. Based on the current estimate, even including the follow-up delayed caused by COVID-19, the inevaluable rate is still within 19%. Note that patients who were randomized but never started treatments will be replaced if the inevaluable rate is above 19%.

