SETER/PR index: estrogen related transcription  
Ki-67, COX-2, p16, CD68.
6. To examine whether any reductions in mammographic density seen after 1 year of 4-OHT vs. placebo gel application persist at 24 months (or longer under the COVID-19 Contingency Plan), one year after gel application has stopped.

All available data will be summarized and analyzed for the secondary analysis. At the end of the study, participant demographic characteristics; the following measurements at baseline and 52 weeks: 1) MD of the breast, 2) tissue biomarkers (among women undergoing optional pre- and post-treatment biopsies: TDLU Involution, Collagen structural changes, SET index, Ki-67, COX-2, p16, CD68, etc.), 3) plasma measurements of parent drug and related metabolite levels and factors related to 4-OHT exposures, such as IGF pathway members, CRP, estradiol, bisphenol and 4-OHT; and the percentage of women with  $\geq 10\%$  absolute decrease in percent MD between baseline and 52 weeks will be summarized using descriptive statistics, such as mean, standard deviation, median and range for continuous variables and frequency/percentage for discrete variables. The difference of continuous variables between baseline and 52 weeks may be compared between two groups using t-test or Wilcoxon rank sum test, whichever is appropriate. Multivariate analogues to the before mentioned univariate tests, such as Hotelling's  $T^2$  test and multivariate multiple regression will be employed when appropriate. Transformation may be performed when necessary to make continuous variables close to normal distribution before evaluating the change of these continuous variables over time between two groups using repeated measures analysis where the intra-participant correlation is taken into consideration, adjusting for other important covariates. In addition, longitudinal data analysis such as the linear mixed effect model will be applied to evaluate the mammogram density change over time. The treatment effect will be evaluated adjusting for other important covariates. The effect of compliance will be evaluated in the per protocol analysis.

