### **13.6 Reporting and Exclusions**

Every reasonable attempt will be made to recover any missing data. If any data for the primary efficacy measure remains missing, then the change of the primary endpoint will not be calculated, and the participant will not be evaluable for the primary endpoint. We will also consider multiple imputations using predictive values based on regression models under the assumption of missing at random to supplement the primary analysis. In addition, any available data will be included in the repeated measure analysis for both primary and secondary endpoints, which allows for all participants with complete or partial data.

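### The primary Hotelling's T-squared test adjusts for neither baseline density nor the randomisation strata: it is valid and unbiased, but can give up precision

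*Combined protocol and SAP*

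**What the plan says.** Section 13.4 makes a two-sample Hotelling's T-squared test on the MLO and CC changes from baseline the primary comparison. It says the "test represents the multivariate generalization to the independent two-sample t-test in the univariate setting". No covariate or stratum term is named. Baseline density enters only because it is subtracted.

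Section 13.2 stratifies the allocation: "We will stratify the randomization by study site" (seven centres) and by density category C or D, in permuted blocks of 4. Section 13.4 defines the analysed women as "all participants who are randomized and have MD measurements from both baseline and 52 weeks", so none lacks the baseline value.

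Other models are planned:

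- Section 13.4 examines C versus D "by incorporating this covariate and its interaction with treatment over time in the repeated measures analysis". This asks about effect modification.
- Section 13.4 also allows timing of the mammogram as a covariate where appropriate, to look at prolonged exposure.
- Section 13.5, on secondary analyses: "The treatment effect will be evaluated adjusting for other important covariates". The covariates are not named. It also allows multivariate multiple regression or MANOVA where appropriate.
- Section 13.6: "any available data will be included in the repeated measure analysis for both primary and secondary endpoints".

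None of these is the primary test, none names site, and none names continuous baseline density as a covariate.

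**The concern.** Factors that restrict the randomisation, and a baseline measure of the outcome itself, are the usual covariates for a primary comparison. Leaving them out does not bias the estimate. If strata predict change, the unadjusted test is slightly conservative, because its standard error ignores the balance that stratification created. If baseline density or site predicts change, the interval is wider and the power lower than the collected data allow.

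The design has little slack: 80% power at 64 evaluable women per arm. Section 2.3 also gives the estimate a further use: "Preliminary information gained from this study will enable us to plan a prospective, large, national study". Its precision therefore matters beyond the significance test.

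**Working it through.** **Inputs from the documents.** Section 13.1 sets decreases of 6% and 2% (a difference of 4 points) "with a common standard deviation of 8%, using a two-sided t-test with a significance level of 0.05", with 64 evaluable women per arm. Section 13.2 gives 158 randomised, seven sites, two categories and blocks of 4.

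**Inputs assumed, because the documents do not give them.** These are the baseline-to-Month 12 correlation r (0.7 to 0.95), equal SDs at the two times, the MLO-CC correlation ρ (0.5 to 0.9), the share of variance explained by site (0 or 5%), and the same 4-point effect and SD of 8 in both views.

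**Step 1: the plan's own figure.** The noncentrality is 4/(8·√(2/64)) = 2.83 on 126 df. Exact two-sided t-test power is 80.1%, which reproduces the stated 80%.

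**Step 2: adjustment on that t-test basis.** With equal SDs, the variance ratio of baseline-adjusted to change-score analysis is (1+r)/2. Eight covariate df are charged (baseline 1, category 1, site 6), leaving 118. Extra women = 128/((1+r)/2) − 128. The unadjusted 95% CI half-width is 1.979·8·√(2/64) = 2.80 points.

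| r | Variance ratio | Residual SD | Power | Half-width | Worth in extra women |
|---|---|---|---|---|---|
| 0.7 | 0.85 | 7.38 | 86.1% | 2.58 | 22.6 |
| 0.8 | 0.90 | 7.59 | 84.1% | 2.66 | 14.2 |
| 0.9 | 0.95 | 7.80 | 82.1% | 2.73 | 6.7 |
| 0.95 | 0.975 | 7.90 | 81.1% | 2.77 | 3.3 |

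This charges df but not chance covariate imbalance, and it is not the planned test. It is an upper guide to the baseline gain under equal SDs.

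**Step 3: the planned T-squared test.** With d = 4/8 = 0.5 in both views, the noncentrality is (64/2)·2·0.5²/(1+ρ) = 16/(1+ρ). At ρ = 0.7 this is 9.41 on (2, 125) df, and power is 78.0%. Charging nine df (both views' baselines) with no variance gain gives 77.9%, so the df alone cost under 0.1 point.

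**Step 4: simulation of T-squared, unadjusted against adjusted.** There were 30,000 runs per cell with stratified permuted blocks, unequal sites (assumed shares from 34% down to 5%), category generated from baseline with noise, 19% lost at random and ρ = 0.7. The adjusted model has both views' baselines, category and site.

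| r | Site explains 0% | Change | Site explains 5% | Change |
|---|---|---|---|---|
| 0.7 | 78.5 → 83.2% | +4.7 | 78.8 → 85.6% | +6.8 |
| 0.8 | 78.1 → 80.8% | +2.6 | 78.4 → 83.2% | +4.7 |
| 0.9 | 78.0 → 78.6% | +0.6 | 77.8 → 80.6% | +2.7 |
| 0.95 | 78.1 → 77.7% | −0.4 | 77.9 → 79.6% | +1.7 |

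Changes were taken before rounding; their Monte Carlo SE is 0.12 to 0.18 points. Break-even with no site effect is near r = 0.93. With no predictive covariate, power goes from 77.5% to 76.2% (−1.3). At ρ = 0.5 or 0.9 the gain is +4.0 or +5.0 at r = 0.7, and +0.6 or +0.7 at r = 0.9. A repeat simulation with no site effect gave about +4.7, +2.9, +1.2 and −0.3 across the four r values, and −1.7 with nothing predictive.

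**Step 5: validity.** Simulated size of the unadjusted test is 4.4 to 4.8% if site explains 5%, and 4.7 to 5.0% if it explains nothing. The adjusted test gives 4.9 to 5.1%. In a separate simulation (4,000 runs per scenario), unadjusted estimates of a true −4 averaged −3.98 to −4.03.

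**The case against.** The strongest reply is that nothing here is an error. The sample size and the primary test are both unadjusted and so agree with each other, and the sign of the gain is not determined by anything in the documents. That is fair, and it is why the point concerns efficiency only.

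The equal-SD assumption also matters. The general variance ratio is k²(1−r²)/(1+k²−2rk), where k is the follow-up SD divided by the baseline SD. At r = 0.9 with the change SD held at 8, k = 1.1 gives 1.00 and t-test power of 80.1%, so no baseline gain. k = 0.9 gives 0.81 and 87.6%. The uncertainty is therefore wider than the tables show, in both directions.

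It can also be said that Section 13.5 already allows multivariate regression, the right class of model. It does, but optionally, without naming covariates and outside the primary test.

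Lastly, this is a late version (Version 20, 02/07/2022), and Section 6.9 leaves the statistician unblinded, so a changed primary test could look data-driven. That deserves a safeguard. The risk is limited because the proposed covariates are the randomisation strata and the baseline outcome, not variables picked from the results.

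**Conclusion.** The point holds, as a recommendation about precision. The unadjusted test is valid and unbiased as regards adjustment, and at most slightly conservative. This says nothing about restricting the analysis to women with both mammograms, which is a separate matter; the simulations assumed loss at random.

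Under the assumed inputs with equal SDs, adjusting the planned test changes power by between −0.4 and +6.8 points at ρ = 0.7. The loss is about 1.3 to 1.7 points if no covariate predicts change. Baseline and stratum gains overlap and must not be added. The balance favours adjustment, but the gain could be negligible, so confidence in its size is only medium.

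**What to change.** Before database lock, specify the primary comparison with treatment, continuous baseline percent density, category C/D and site as main effects.

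- If both views stay a joint outcome, use MANCOVA, the adjusted form of T-squared. If the mean of the two views is adopted for other reasons, use ANCOVA.
- Pool small sites by a stated rule. For example, put all sites with fewer than 8 evaluable women (two blocks of 4) into one level.
- State how the Box-Cox step in Section 13.4 applies to the adjusted model, including the scale of the baseline covariate.
- Report the adjusted difference with its 95% CI, or simultaneous intervals if both views are kept. Keep the unadjusted test as a sensitivity analysis.
- Record that the change was made without reference to outcome data by arm, given the unblinded statistician.

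The cost is SAP wording, plus 8 covariate df (9 with both views' baselines) out of about 126. All covariates are already collected.

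### The 80% power belongs to a t-test and is not a lower bound for the primary Hotelling's T² test, whose power at 64 per arm may be as low as 71%

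*Combined protocol and SAP*

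**What the plan says.** Section 13.1 gives the sample size: "With 64 women in each group, we will have an 80% power to detect a decrease of percent MD of 6% in treatment group". The comparison is with a 2% decrease on placebo, and the test is specified "with a common standard deviation of 8%, using a two-sided t-test with a significance level of 0.05". This is a one-variable calculation.

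Section 13.4 defines percent density as "visually estimated using both the mediolateral oblique (MLO) view and the craniocaudal (CC) view as the proportion of the total breast area" occupied by dense tissue. It then names Hotelling's T², a bivariate test, as primary: "The mean change in percent MD at 52 weeks incorporating both the MLO and CC views will be compared between the two groups utilizing" this method. On dependence between the views it says only this: "The correlation and variance-covariance matrix will be assessed to estimate the level of dependency between the MLO and the CC views".

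The link between the sizing and the primary test is the closing statement of the same paragraph. It begins "Note that the sample size calculation is based on the two-sample t-test. It provides a conservative estimate of the statistical power because the" and rests on one reason, namely that the bivariate "test is more efficient than the two-sample t-test".

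The statistical section gives no power for T², no design value for the correlation between the MLO and CC changes, no effect for each view, and no statement of whether the SD of 8% is per view or for the two-view measure.

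**The concern.** The closing statement carries no condition, so a reader takes 80% as the least power the primary test can have. T² has no such general advantage. It looks for a difference in any direction in two dimensions and pays for that with a higher critical value. Whether the second view repays the cost depends on the correlation between the views, the effect in each view, and what the SD of 8% refers to. The plan fixes none of these.

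At stake is how a null primary result is read. The plan implies that a true 4-point effect would be missed at most 20% of the time. If the real figure is nearer 29%, a null result rules out less than readers will think. Section 2.3 also says the trial is meant to inform a larger national study, which could inherit the same reasoning.

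**Working it through.** **Inputs.** From Section 13.1: 64 evaluable per arm, difference 6 − 2 = 4 points, common SD 8, two-sided 0.05. From Section 13.4: T² with two variables, the MLO and CC changes. The correlation r between the two changes is not given, so every value of r below is an assumption.

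**The plan's own figure.** Standardized effect 4/8 = 0.5; noncentrality 0.5 × √(64/2) = 2.828; noncentral t with 126 df. Power = 80.1%, so the stated 80% is right for the t-test. On the squared scale the noncentrality is 2.828² = 8.0.

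**T² formula.** T² × 125/(2 × 126) follows F(2, 125) with noncentrality λ = (64/2) × δ′S⁻¹δ, where δ holds the two view effects and S is the covariance matrix of the two changes. With effects e₁ and e₂ and a common view SD s,

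λ = 32 × (e₁² + e₂² − 2r·e₁e₂) / [s²(1 − r²)].

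The critical value of F(2, 125) is 3.069, which is 6.19 on the T² scale. The squared t critical value is 1.979² = 3.92. Power of 80% needs λ = 9.87, against the 8.0 that is enough for the t-test.

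**Reading (a): SD 8 is for the two-view percent density; equal effects and SDs in both views.** If the two-view measure is the mean of the views, each view's SD satisfies s²(1 + r)/2 = 64, and λ = 32 × 2 × 16/[s²(1 + r)] = 8.0 whatever r is. Power = **70.6%**. To reach 80% takes 79 evaluable per arm, or 158 in all; at 19% attrition 158/0.81 = 195.1, so about 196 randomized against the planned 158.

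**Reading (b): effect 4 and SD 8 in each view.** λ = 16/(1 + r).

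| r | λ | T² power | t-test on the view average |
|---|---|---|---|
| 0 | 16.0 | 95.2% | 97.8% |
| 0.3 | 12.3 | 88.4% | 93.6% |
| 0.5 | 10.7 | 83.2% | 90.0% |
| 0.6 | 10.0 | 80.5% | 88.1% |
| 0.7 | 9.4 | 78.0% | 86.1% |
| 0.8 | 8.9 | 75.5% | 84.1% |
| 0.9 | 8.4 | 73.0% | 82.1% |
| 0.95 | 8.2 | 71.8% | 81.1% |

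Power is 80% where 16/(1 + r) = 9.87, that is r = 0.62. Evaluable women per arm needed for 80%: 60 (r = 0.5), 68 (0.7), 71 (0.8), 75 (0.9). Simulation of 40,000 trials per setting gave 83.2%, 75.6% and 72.8% at r = 0.5, 0.8 and 0.9.

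**Unequal view effects, mean still 4 points (4.5 and 3.5).**

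| r | Reading (a) | Reading (b) |
|---|---|---|
| 0.8 | 76.6% | 81.1% |
| 0.9 | 82.1% | 84.1% |
| 0.95 | 89.8% | 90.6% |

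So unequal effects can lift T² above 80% under either reading.

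**The floor.** λ for T² is never less than that of any single view or of the view average. If any one of these has a standardized effect of 0.5, then λ ≥ 8.0 and T² power is at least 70.6%. A miss rate of about 29% (100 − 70.6) is therefore the worst case under the design effect.

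**The case against.** The strongest reply is that T² can beat the t-test, and that the worst figures need equal effects in the two views, which the documents do not assert. This is correct. With a 4.5/3.5 split T² passes 80% under reading (a) at r = 0.9, and under reading (b) it is above 81% at 0.8, 0.9 and 0.95. High correlation is also where a small difference between views helps T² most. It shows that the claim is sometimes true. It does not rescue a statement made without conditions, because equal effects at r above 0.62, or reading (a) with equal effects, contradict it.

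A second reply is that no correlation is given, so no shortfall is proven. That also stands as far as it goes: the actual power cannot be fixed from the documents, and 29% is the end of a range and not an estimate. But the same gap removes any basis for calling 80% conservative. The plan's intention to assess the correlation from trial data does not by itself show that it was ignored at design; its statement that the sizing used the t-test does.

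A third reply is that the harm is limited. T² is valid at the 0.05 level, Section 13.4 calls for arm-level summaries and a 95% confidence ellipse, Section 13.8 asks for 95% confidence intervals, Sections 13.5 and 13.6 add mixed-model and repeated-measures analyses, and this is a phase II trial. These points bear on severity. They do not make the power statement correct.

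**Conclusion.** The concern holds. The 80% is correct for the two-sample t-test and is not a lower bound for the primary T² test. At 64 per arm and a 4-point difference, T² power is 70.6% if the SD of 8 is for the two-view measure with equal view effects and SDs. If the effect and SD apply to each view, it runs from 95.2% down to 71.8% as r goes from 0 to 0.95, crossing 80% near r = 0.62. Unequal view effects can move power up or down. All T² figures are conditional on inputs the plan does not state. The type I error of the primary test is unaffected. This should be fixed, but it does not threaten the trial's validity.

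**What to change.** **Required.** In Section 13.4, delete the sentence on conservatism and efficiency. State that the 80% in Section 13.1 is the power of a two-sample t-test. Add a short table of T² power at 64 evaluable per arm, naming the assumed MLO–CC correlation of change, the effect in each view, and whether the SD of 8% is per view or for the two-view percent density. The cost is wording and one table; nothing changes in data, visits or sample size.

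**Optional.** Make a two-sided t-test or ANCOVA on the change in the MLO/CC average the primary analysis and keep T² as supportive. With equal view effects the t-test has at least 80% power at every correlation: 80.1% under reading (a), and the last column of the reading (b) table. This costs more. The protocol is at Version 20, Section 14.3 requires approval of an amendment, and Section 6.9 leaves the statistician unblinded, so the change would have to be settled before any unblinded analysis. It also gives up sensitivity when effects differ between views: with 4.5/3.5 at r = 0.9 under reading (b), 82.1% for the average against 84.1% for T². The required fix does not depend on it.
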